## **7 Safety and Adverse Events**

### **7.1 Definitions**

#### **7.1.1 Adverse Event**

An adverse event (AE) is any symptom, sign, illness or experience that develops or worsens in severity during the course of the study. Intercurrent illnesses or injuries should be regarded as adverse events. Abnormal results of diagnostic procedures are considered to be adverse events if the abnormality:

- results in study withdrawal
- is associated with a serious adverse event
- is associated with clinical signs or symptoms
- leads to additional treatment or to further diagnostic tests
- is considered by the investigator to be of clinical significance

#### **7.1.2 Serious Adverse Event**

#### **Serious Adverse Event**

Adverse events are classified as serious or non-serious. A serious adverse event is any AE that is:

- fatal
- life-threatening
- requires or prolongs hospital stay

- results in persistent or significant disability or incapacity
- required intervention to prevent permanent impairment or damage
- a congenital anomaly or birth defect
- an important medical event

Important medical events are those that may not be immediately life threatening, but are clearly of major clinical significance. They may jeopardize the subject, and may require intervention to prevent one of the other serious outcomes noted above. For example, drug overdose or abuse, a seizure that did not result in in-patient hospitalization, or intensive treatment of bronchospasm in an emergency department would typically be considered serious.

All adverse events that do not meet any of the criteria for serious should be regarded as non-serious adverse events.

## **7.2 Recording of Adverse Events**

At each contact with the subject, the investigator will seek information on adverse events by specific questioning and, as appropriate, by examination. Information on all adverse events will be recorded immediately in the source document, and also in the appropriate adverse event module of the case report form (CRF). All clearly related signs, symptoms, and abnormal diagnostic procedures results should be recorded in the source document, though should be grouped under one diagnosis.

All adverse events occurring during the study period will be recorded. The clinical course of each event will be followed until resolution, stabilization, or until it has been determined that the study intervention or participation is not the cause. Serious adverse events that are still ongoing at the end of the study period will be followed up to determine the final outcome. Any serious adverse event that occurs after the study period and is considered to be possibly related to the study intervention or study participation will be recorded and reported.

## **7.3 Relationship of AE to Study**

The PI and safety monitor will be jointly making the determination the relationship of each adverse event to the study procedure. Prior studies have described AE's common to this procedure to be nausea, emesis, and hypotension (Brown et al., 2019). These will be considered to be probably or definitely related to the procedure, after analysis of the data is considered. Other AEs will be determined and characterized on a case by case basis.

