### **1.1 Background and Relevant Literature**

Significant postoperative pain following craniotomy affects more than 80% of patients (Mordhorst et al., 2010) and adversely affects patient satisfaction (Myles, Williams, Hendrata, Anderson, & Weeks, 2000). Inadequate post-operative pain control can lead to patient distress, increased sympathetic activity, elevated vital signs (e.g. heart rate, respirations, and blood pressure), increased intracranial pressure and intracerebral hemorrhage. The current standard of care is to manage focal cranial pain with systemic opiate medications, such as morphine and hydromorphone. While systemic administration of opiate medications may achieve a tolerable level of analgesia, they are associated with a degree of risk. Systemic opiates induce respiratory depression, nausea, vomiting, pruritis, hypotension, and sedation, while simultaneously masking the neurological examination (Lai, Ortiz-Cardona, & Bendo, 2012). These opioid-related side effects often lead to a significant increase in total hospital cost, length of stay and acuity of medical care (Oderda et al., 2007). This is contrary to the generally accepted practice of minimizing ICU length of stay for patient safety and cost containment purposes (Beauregard & Friedman, 2003). Postoperative pain is a critical barrier to patient safety and cost effectiveness following routine cranial procedures.

Regional scalp anesthesia for local pain control offers the potential to minimize side effects of systemic opiates while affording patient comfort. Regional scalp analgesia is a safe and effective way of preventing pain during cranial surgery. Using a 1:1 mixture of lidocaine (1% with 1:200,000 epinephrine) and bupivacaine (0.5%), the PI of this proposal routinely performs hemicranial regional blocks for craniotomies at the Hospital of the University of Pennsylvania. Patients are sufficiently comfortable following regional hemicranial block to maintain normal vital signs with low pain scores and participate in complex neuropsychological testing during the operation.

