The side effect profile of liposomal bupivacaine is similar to bupivacaine HCL and occurs with similar frequency (8-20%) (Baxter, Bramlett, Onel, & Daniels, 2013). Described local toxicities have included granulomatous inflammation, myocyte toxicity, chondrotoxicity and intervertebral disc cell cytotoxicity (Brown & Morrison, 2004; Richard et al., 2011). Some of these toxicities are associated with local anesthetic infusion pumps (Brown and Morrison, Anesthesiology 2004), while others are associated with direct intra-articular or intra-discal injections (Chu, Izzo, Coyle, Papas, & Logar, 2008). Systemic toxicity of liposomal bupivacaine is similar to bupivacaine HCL. Known systemic toxicities of bupivacaine include prolongation of QTc intervals and seizures with high dose, intravenous injection (Naseem et al., 2012). Adverse events associated with liposomal bupivacaine usage were nausea, emesis and hypotension, while showing reductions in constipation, urinary retention and pruritus relative to standard opioid treatment (Brown et al., 2019).

The long-lasting nature of liposomal bupivacaine makes it an attractive candidate for long-lasting postoperative pain relief following supratentorial craniotomy. This study focuses on comparing this novel agent with traditional local anesthetic in producing durable and effective analgesia in cranial blocks after craniotomy.

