### **3.3 Study Measures**

A 10-cm VAS (where '0' is defined as 'no pain at all' and '10' as 'the worst possible pain' will be used to assess subjects' pain score. This will be assessed every 2 hours after extubation postoperatively while the patient is in the ICU, and every 4 hours after the patient has left the ICU, for 72 hours while inpatient, during waking hours, or until discharge in patients discharged prior to 72 hours post-op.

The Glasgow Coma score (GCS) (Teasdale & Jennett, 1974) will also be assessed at the above time points. Patients with GCS verbal score of <4 will be excluded from statistical analysis because of inability to respond to questions after extubation.

The cumulative doses of narcotics during this time period will also be measured. Intravenous narcotic medications will be given by the nurse taking care of the patient as rescue analgesic, as requested by the patient. If the patient requires more analgesics, the dosage will be increased as needed by the patient following standard clinical guidelines. Nursing personnel will be instructed to administer analgesic according to patient demand. The total rescue analgesic requirement will be noted at the above mentioned time intervals.

The duration of time between the end of the surgical procedure (extubation) and the first administration of rescue narcotic will be recorded.

The total length of ICU stay will be recorded. The total length of hospital stay will also be recorded.

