## **6.2 Statistical Methods**

The primary and secondary outcome variables will be examined for group-wise differences with Analysis of Variance statistics. Significant differences in the means will then be subjected to Bonferroni's t-test. Pearson correlation coefficients will be computed for associations between variables. A p-value of <0.05 will be regarded as statistically significant.

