The cardiac toxicity profile of liposomal bupivacaine subcutaneous injection both in healthy volunteers and in patients undergoing total knee arthroplasty has also been reviewed (Bergese, Onel, Morren, & Morganroth, 2012; Naseem et al., 2012). Four doses (150, 300, 450, or 600 mg) of liposomal bupivacaine were compared to bupivacaine HCl with epinephrine injected. There were no significant differences in change from baseline in QRS or QTc duration between the two groups, nor did they differ in mean change from baseline heart rate and PR interval. In healthy volunteers receiving 300, 450, 600, and 750 mg subcutaneous injection, none of the participants had a maximum QTc interval greater than 500 ms, and there were no changes in QTc of greater than 60 ms at any measured time point.

[name] will verbally report adverse events of any type in patients enrolled in this study to the University of Pennsylvania IRB and Study Officer within 24 hours of the time of the event. The event will then be documented in detail and submitted in writing within 10 days. Any adverse event that might occur would more likely be related to clinical causes than to this study.

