### 10.2 Benefits

Participation in this research offers the potential benefit of more effective and/or longer-lasting pain relief after surgery, a decreased need for narcotics, avoidance of unnecessary invasive intracranial monitoring, avoidance of exposure to radiation related to CT scans, a shorter ICU stay and/or shorter hospital stay. A decreased narcotic requirement may prevent the common side effects of respiratory depression, nausea, vomiting, pruritis, hypotension, and sedation. Further, it may allow for more prompt and more accurate neurological exams to be conducted by the healthcare team, which may prevent potential adverse postsurgical events.

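### Section 7.3 presumes that nausea, emesis and hypotension are related to the procedure in every arm, with no criterion for rebuttal and no planned by-arm adverse event table

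*Combined protocol and SAP*

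**What the plan says.** Section 7.3 has the PI and the safety monitor jointly determine how each adverse event relates to the study procedure. It names nausea, emesis and hypotension as common to the procedure, citing one prior study, and then says: "These will be considered to be probably or definitely related to the procedure, after analysis of the data is considered". The next sentence gives the rest a different route: "Other AEs will be determined and characterized on a case by case basis".

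Other sections bear on the same three events:

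- Section 1.1, citing the same study, ties them to one drug: "Adverse events associated with liposomal bupivacaine usage were nausea, emesis and hypotension".
- Section 1.1 also lists them as opioid effects: "Systemic opiates induce respiratory depression, nausea, vomiting, pruritis, hypotension, and sedation".
- Section 10.2 offers fewer of them as a possible benefit: "A decreased narcotic requirement may prevent the common side effects of respiratory depression, nausea, vomiting, pruritis, hypotension, and sedation".
- Section 3.3 makes opioids available on demand without distinguishing arms: "Intravenous narcotic medications will be given by the nurse taking care of the patient as rescue analgesic, as requested by the patient".
- Section 6.2 limits the between-group analysis: "The primary and secondary outcome variables will be examined for group-wise differences with Analysis of Variance statistics". Adverse events are not among the outcomes in sections 3.4.1 and 3.4.2, and section 6.2.2 adds none.

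**The concern.** A relatedness label should follow from the facts of the case. Here three events start from a presumption of relatedness, and the protocol's own text supplies a competing cause for each. Every patient has a craniotomy under general anaesthesia and may ask for intravenous opioids. The wording names no arm, so a saline patient who vomits after rescue opioid falls under the same presumption as a patient given liposomal bupivacaine.

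What is at stake is how these events are read at the end of the trial. If the block spares opioids, as section 10.2 hopes, nausea, vomiting and hypotension may become less frequent in the active arms. The cases that remain would be presumed related to the block, and no planned table would set them against saline. The label says nothing about whether the block raised or lowered the event rate. The randomised comparison can speak to that, and the plan does not include it for adverse events.

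**Working it through.** The plan gives no figure for this point, so there is none to reproduce. The check has two parts.

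**Text**

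1. *Is there a separate rule?* Yes. Section 7.3 states a presumption for three events and sends only the others to case-by-case judgement.
2. *Can it be rebutted?* Yes. The joint determination covers each event, and the quoted sentence makes the outcome subject to a look at the data. No criterion is given, and section 6 specifies no adverse event analysis that could supply one.
3. *Does the cited evidence support it for this block?* Weakly. By its title in the reference list, the cited study concerns liposomal bupivacaine in elective spine surgery. Section 6.1 says that liposomal bupivacaine had not been studied for pain after craniotomy. Neither statement supports a presumption for plain bupivacaine or saline.
4. *Is there a competing cause in every arm?* Yes: systemic opioids (sections 1.1 and 10.2), given on request (section 3.3).

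**Size**

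Inputs: 90 patients (section 4.1) allocated 1:1:1 (section 3.2), so 30 per arm and 60 on active drug. The documents give no all-cause rates by arm. Section 10.1 has only treatment-related rates from other studies. The rates p below are therefore assumptions, with each patient counted once.

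*No block effect, same rate in all arms.* The most that can be coded related is 60p on active drug and 30p on saline. The randomised excess is 60 × (p − p) = 0.

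| Assumed rate | Active (60p) | Saline (30p) | Total | Excess over saline |
|---|---|---|---|---|
| 10% | 6 | 3 | 9 | 0 |
| 30% | 18 | 9 | 27 | 0 |
| 50% | 30 | 15 | 45 | 0 |

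*Benefit example, 50% on saline and 30% on both active drugs.* At most 0.30 × 60 + 0.50 × 30 = 18 + 15 = 33 cases are coded related. The active arms have (0.50 − 0.30) × 60 = 12 fewer cases than the saline rate predicts.

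*Precision of a by-arm table.* With Wilson limits (l, u) for each arm and D = p1 − p2, the Newcombe score interval is

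lower = D − √[(p1 − l1)² + (u2 − p2)²], upper = D + √[(u1 − p1)² + (p2 − l2)²].

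For 9/30 versus 9/30 the Wilson limits are 0.167 and 0.479 in each arm, so the half-width is √[(0.300 − 0.167)² + (0.479 − 0.300)²] = √(0.0178 + 0.0320) = 0.223. The rest follow in the same way:

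| Comparison | Difference | 95% interval (points) |
|---|---|---|
| 3/30 v 3/30 | 0 | −16.9 to +16.9 |
| 9/30 v 9/30 | 0 | −22.3 to +22.3 |
| 15/30 v 15/30 | 0 | −23.8 to +23.8 |
| 6/60 v 3/30 | 0 | −16.5 to +12.1 |
| 18/60 v 9/30 | 0 | −20.5 to +18.3 |
| 30/60 v 15/30 | 0 | −20.8 to +20.8 |
| 18/60 v 15/30 | −20 | −39.6 to +1.0 |
| 9/30 v 15/30 | −20 | −41.5 to +4.6 |

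**The case against.** The strongest reply is that little turns on the label, and most of that reply stands.

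- *The presumption is not an automatic code.* A reader might infer that every case must be coded related. The text does not support that. Each event is determined jointly, and the data are to be considered. Section 7.2 allows follow-up to end once the intervention is judged not to be the cause. Section 7.4.1 provides for a revised assessment on new information, with concomitant medication as an example, and rescue opioid would qualify. The counts above are therefore upper limits.
- *No planned output or main safety action depends on it.* No summary by relatedness is planned. Section 10.1 has events of any type reported to the IRB within 24 hours, and sections 5.6, 7.4.2 and 9.1 stop enrolment on any suspected event. Section 7.4 ties prompt IRB notice to relatedness, but that adds little to these.
- *It is cautious and arm-neutral.* Saline patients also receive the needle infiltration, which the word procedure can cover. Case-by-case judgement would be made by a safety officer who sees drug group and a PI who may have been the unblinded surgeon. This is a real cost of removing the presumption.
- *Opioid side effects are not an endpoint.* Narcotic requirement is, and it is compared between arms.

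A reader might also take the remark in section 10.1, "Any adverse event that might occur would more likely be related to clinical causes than to this study", as a rule that contradicts section 7.3. It is a general comment in a risks section, not a classification rule, and the point does not rest on it.

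What the reply leaves untouched is the different treatment of three events that the protocol itself attributes to opioids, the lack of a criterion for rebuttal, and the lack of any by-arm tabulation. The safety officer's unblinded reviews at 5, 20, 40 and 60 subjects lessen the last gap but specify no table.

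**Conclusion.** The point holds as a minor one. Section 7.3 sets a rebuttable presumption, without a criterion for rebuttal, that nausea, emesis and hypotension are related to the procedure in all three arms. With no planned comparison by arm, a related count for these events could credit opioid or surgical effects to the block. With no block effect, at most 9, 27 or 45 patients of 90 would be so coded at assumed rates of 10%, 30% or 50%, although the randomised excess is zero. These figures rest on assumed rates and on the presumption being upheld in every case.

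The documents do not support reading this as a threat to the pain endpoint, the sample size, IRB reporting or patient protection. Nor would a by-arm table settle attribution: at 30 per arm it gives estimates with wide intervals. Its value is that it uses the randomised comparison and does not depend on what the assessors knew about the arm. It is the more useful half of the remedy.

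**What to change.** 1. **Section 7.3.** Delete the two sentences that single out nausea, emesis and hypotension. State that the PI and safety monitor will judge every adverse event case by case as unrelated, possibly, probably or definitely related, taking rescue opioid use into account.
2. **Section 6.2.** Add a descriptive table of adverse events, including nausea, vomiting and hypotension, by randomised arm and regardless of relatedness, for all patients who received a block. Give n (%) per arm and risk differences with 95% score intervals for each active arm versus saline and for both active arms versus saline.

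Deleting the closing remark on likely causes in section 10.1 is optional tidying.

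The cost is a few sentences and one table, from data already recorded under section 7.2. No visits, patients or adjudicators are added, and the sample size and alpha do not change. The downsides are a little more analysis, wide intervals, and case-by-case judgement by assessors who may know the arm. The last is why the table should ignore relatedness.

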## **7.4 Reporting of Adverse Events and Unanticipated Problems**

The Investigator will promptly notify the Penn IRB of all on-site unanticipated problems and adverse events that are related to the research activity. Other unanticipated problems related to the research involving risk to subjects or others will also be reported promptly. Written reports will be filed using the HS-ERA and in accordance with the Penn IRB timeline of 10 working days.

#### **7.4.1 Follow-up Report**

If an AE has not resolved at the time of the initial report and new information arises that changes the investigator's assessment of the event, a follow-up report including all relevant new or reassessed information (e.g., concomitant medication, medical history) will be submitted to the IRB. The investigator is responsible for ensuring that all SAEs are followed until either resolved or stable.

#### **7.4.2 Data and Safety Monitoring Plan**

A local safety officer will have access to unblinded data, including patient identification and drug group. [name], MD, PhD, has extensive experience with randomized controlled studies, and has served in the capacity of Safety Officer for studies. [name], in collaboration with the study coordinator, will review patient data once five subjects have been enrolled. When 15 additional subjects have been enrolled for a total of 20, [name] will again review the data. Reviews will continue at increments of 20 subjects, at enrollment totals of 40 and 60. Specifically, the Safety Officer will independently examine the primary outcome measure (i.e. cumulative pain intensity scores) and secondary outcome measures (i.e. GCS, narcotic utilization, time to rescue medication, ICU length of stay, hospital length of stay), as well as remain vigilant for any adverse events. If any adverse events are suspected, enrollment will immediately cease, the IRB will be notified, and a meeting between the Safety Officer, PI, and study coordinator will take place.

[name] contact information will be provided on the study instruction sheet provided to nurses and available in the patient's chart. If any clinical staff suspects an adverse event, the study sheet provides instructions to contact the IRB and [name] immediately. Additional contact information for the PI, and the study coordinator, will be listed for any concerns.

### **8 Study Administration, Data Handling and Record Keeping**

#### **8.1 Confidentiality**

Information about study subjects will be kept confidential and managed according to the requirements of the Health Insurance Portability and Accountability Act of 1996 (HIPAA). Those regulations require a signed subject authorization informing the subject of the following:

- What protected health information (PHI) will be collected from subjects in this study
- Who will have access to that information and why
- Who will use or disclose that information
- The rights of a research subject to revoke their authorization for use of their PHI.

In the event that a subject revokes authorization to collect or use PHI, the investigator, by regulation, retains the ability to use all information collected prior to the revocation of subject authorization. For subjects that have revoked authorization to collect or use PHI, attempts should be made to obtain

permission to collect at least vital status (i.e. that the subject is alive) at the end of their scheduled study period.

## **8.2 Data Collection and Management**

Confidentiality of the collected data will be maintained in the following ways:

- Paper-based records will be kept in a secure location and only be accessible to personnel involved in the study.
- Computer-based files will only be made available to personnel involved in the study through the use of access privileges and passwords.
- Prior to access to any study-related information, personnel will be required to sign statements agreeing to protect the security and confidentiality of identifiable information.
- Whenever feasible, identifiers will be removed from study-related information.

All data is stripped of any and all identifying information and stored with code numbers as a reference. Names and participant numbers only appear together on a single master list that will reside in a password-protected file within the Neurosurgery Clinical Research Division (NCRD), accessible to only authorized personnel. Access to all files will be restricted to the Principal Investigator and his research team. All team members have completed both the University of Pennsylvania School of Medicine Patient-Oriented Research Certification Program (or the newer CITI Responsible Conduct of Research course) and the NIH-sponsored Human Participant Protections Education for Research Teams or the HIPAA online courses. All lab members have also been carefully instructed in issues related to informed consent and preserving participant confidentiality.

The following protected health information will be collected in order to carry out the research:

- Name
- Medical Record Number

Additional information to be obtained during the study includes:

- Age at the time of surgery
- Sex
- Current working diagnosis
- Other existing medical conditions
- Information from physical examination
- Details of surgical procedure

Data will only be shared with authorized study personnel. Each participant will receive a unique study identification number as a means of de-identifying patient data and maintaining the confidentiality of protected health information (PHI). A master list of study identification numbers and patient names will reside in a password-protected file within the Neurosurgery Clinical Research Division (NCRD).

Recordings obtained from the neurophysiological experiments will be transferred and stored on secure servers as detailed above. The data will be organized by each participant's unique study identification number and devoid of any patient information. Access to this data will be password-protected to ensure that only study personnel are able to view the data.

